Cover Page

Title: Assessing and Promoting Resilience in Patients With Adult Congenital Heart Disease

NCT number: NCT04738474

Document date: Sept 5, 2025

Contents:

Study Protocol

Statistical Analysis Plan

(Research Coordinator's) Study Protocol <last updated 2023>

Specific Aim: Conduct a randomized pilot clinical trial to evaluate the feasibility and preliminary efficacy of the PRISM intervention among patients with ACHD.

Hypothesis: PRISM will be feasible and improve patient-reported resilience compared to usual care.

Description of PRISM sessions:

Topic	Skills	Format
1. Managing Stress	Mindfulness, Relaxation	One-on-One, In-Person or Video Chat
2. Setting Goals	Setting specific and realistic goals, planning for roadblocks	
3. Positive Reframing	Recognizing and replacing negative self-talk	
4. Making Meaning	Identifying benefits, gratitude, purpose, and legacy	
5. Advance Care Planning	Completion of sections of Voicing My Choices™ advance care planning tool for adolescents and young adults	
6. Coming Together	Discussion of what worked, plans for moving forward	Family Meeting
(i) Boosters/Worksheets	Between-session tools & practice	Individual

Questionnaire Elements:

- EuroQOL Scale (EQ5D-3L): 5-item tool used to assess quality of life (QOL) as it relates to health.
- Linear Analog Scale (LAS): Single item tool used to assess QOL on a continuous 0-100 scale.
- Hospital Anxiety and Depression Scale (HADS): 14-item tool to assess symptoms related to anxiety and depression. It is not intended to diagnose these conditions.
- Kessler-6 Psychological Distress Scale: 6-item inventory measuring the level of global psychological distress.
- Advance care planning (ACP) comfort: 2- question assessment of experience and comfort with ACP
- Connor-Davidson Resilience Scale (CD-RISC 10): 10-item measurement of inherent resiliency, created based on the original 25-item tool. Questions revolve around personal problem-solving and approaches to adversity.
- Perceived Competence Scale (PCS): 4-item tool that asks about one's competence in managing disease

Domain	Measurement Tool	Source & Collection Time
Patient-Centered Outcomes		
Quality of Life	EQ5D-3L & LAS (primary)	Patient; enrollment & 3 months
Psychological Distress	HADS; Kessler-6	Patient; enrollment & 3 months
Self-Efficacy (for health)	PCS	Patient; enrollment & 3 months
ACP Comfort	ACP assessment questions	Patient; enrollment & 3 months

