Predictor: Resilience	CD-RISC 10 (primary)	Patient; enrollment & 3 months
Effect Modifier: Health Status	Independence in activities of daily living, presence of heart-related hospitalization in the last year, diagnosis of heart failure	Electronic health record, patient; enrollment

Potential Confounders: Demographics, Social Determinants of Health	Age, sex, race/ethnicity, marital status, education, family structure, residential information, heart lesion severity	Electronic health record, patient; enrollment
--	---	---

General Notes:

RC will keep complete and secure study records and adhere to protocol fidelity

RC will meet with PI **weekly, Thursdays 10am**, to discuss progress and any challenges; RC personal development goals will also be reviewed quarterly

RC will assist in the creation of a secure electronic database and maintain data using REDcap

Study Population:

Adult (18+ years) outpatients receiving care at the UW ACHD clinic

Patients with moderate or complex ACHD, stages C or D (stages A and B excluded; if needed, can expand back to stage B at a later date)

Must be able to participate in study activities independently and in English.

May not have another life-limiting illness or have participated in Aim 2. A life-limiting illness includes any illness known to be acutely terminal. Examples are cancer, Alzheimer's dementia, progressive neuromuscular diseases. RC will discuss with PI if uncertain.

If concern for cognitive impairment, patients will be screened with a six-item screening tool (Callahan 2002): 3-item recall [apple, table, penny], 3-item temporal orientation [day of the week, month, year].

Participant Enrollment:

RC will screen electronic patient lists for ACHD outpatient clinics to identify potential study participants.

RC will contact eligible patients (telephone and email), explain the study, and assess interest in participation using study team written and approved recruitment scripts.

If agreeable, patients will be enrolled into the study. RC will obtain informed consent.

Participants will be randomized to either the “intervention” (completion of PRISM) or “usual care” (non-directive, supportive care without PRISM) groups.

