Randomization will occur following completion of baseline study measures and in a 1:1 ratio. The unit of randomization is the patient, and the randomization group will be the primary predictor of interest (PRISM or “usual care”). Group assignment will be determined using computerized random numbers with variable block sizes. Assignment will be provided to study staff in sealed, opaque, consecutively numbered envelopes (vs built into REDCap).

Participants and the RC will not be blinded; other staff will be blinded to the extent possible. Anticipated sample size of 60 total participants (30 per group). To achieve complete data for 60 participants, we anticipate enrolling 86 patients, 43 in each arm. Enrollment is anticipated within 9 months, may be extended 2-3 months if needed. Goal is to enroll at least 7 patients per month to reach the 1-year maximum.

Planned Enrollment Report

Racial Categories	Ethnic Categories				Total	
	Not Hispanic or Latino		Hispanic or Latino			
	Female	Male	Female	Male		

American Indian/Alaska Native	0	1	0	0	1
Asian	8	8	0	0	16
Native Hawaiian or Other Pacific Islander	1	0	0	0	1
Black or African American	2	2	1	1	6
White	24	24	3	3	54
More than One Race	3	4	0	1	8
Total	38	38	5	5	86

Study Measures and Data Collection:

RC will confirm and document contact information for study follow-up at enrollment.

RC will deliver the baseline questionnaire to all participants.

- Questionnaire will be completed either directly in REDCap via an emailed link, or on paper which will then be transcribed by study personnel into REDCap (if transcribed, will be double checked by another team member).
- At least 5 telephone and email attempts will be made to obtain responses, unless patients opt out
- RC will review responses within one week. If any responses suggest severe participant distress (HADS >16 (?) or K6 >12), RC will discuss with PI immediately.

RC will extract additional pertinent demographic information from medical records

- MRN
- Age
- Sex (Gender*)
- Race
- Ethnicity
- Insurance type
- ACHD diagnosis
- ACHD complexity (A&P classifications)
- Diagnosis of heart failure (or Fontan failure)
- Cardiac hospitalization in last year
- Diagnosis of mood or anxiety disorder (anxiety, depression, bipolar, post-traumatic stress disorder)

Usual Care group:

- No interim interventions apart from routine clinical care
- Direct any study questions to the PI

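### A baseline HADS or K6 score above the protocol's own distress trigger may wait about a week before anyone reads it, and the 3-month form has no stated review rule

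*Combined protocol and SAP*

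**What the plan says.** The rule is in the Study Protocol, Study Measures and Data Collection, in the bullets under the baseline questionnaire. It has two steps. The first is reading: "RC will review responses within one week". The second is escalation: "If any responses suggest severe participant distress (HADS >16 (?) or K6 >12), RC will discuss with PI immediately". The HADS cut-off carries a question mark in parentheses; the K6 cut-off does not.

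The rule covers everyone enrolled: "RC will deliver the baseline questionnaire to all participants". Forms are completed through an emailed REDCap link or "on paper which will then be transcribed by study personnel into REDCap". The protocol does not say whether the week starts at completion, receipt or data entry.

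Questionnaire Elements describes HADS as a "14-item tool to assess symptoms related to anxiety and depression. It is not intended to diagnose these conditions", and K6 as a "6-item inventory measuring the level of global psychological distress". The outcomes table that follows schedules both scales at enrollment and at 3 months. For the 3-month form, the Usual Care and Intervention group lists cover delivery, repeat contact attempts and the gift card. They do not mention reading the answers or escalating a high score.

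**The concern.** The protocol treats a score above the trigger as urgent once it is seen, yet sets a slow deadline for seeing it. A coordinator who follows the text exactly may leave such a score unread for the whole week.

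Three features of the design make this worth attention:

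- Forms can be completed remotely, so no staff member need be present to notice distress.
- Randomization follows completion of the baseline measures, not their review. A participant can be allocated before the score is read.
- The usual-care group has no study intervention before the 3-month questionnaire. For that group, the baseline review is the only described study step before 3 months that would pick up a high score.

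What is at stake is the promptness of participant safety follow-up. The estimated treatment effect is not involved.

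**Working it through.** **Inputs**

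- Review window: one week, start not defined (Study Measures and Data Collection).
- Planned enrollment: 86 (Participant Enrollment).
- Enrollment period: "Enrollment is anticipated within 9 months, may be extended 2-3 months if needed" (same section).
- Scale lengths: 14 items for HADS and 6 for K6 (Questionnaire Elements).
- Next-working-day target: my proposal, not a figure from the documents.

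**Planned enrollment.** With 60 complete participants and the 70% retention in the Statistical Analysis Plan, 60 / 0.70 = 85.7, rounded up to 86. This matches the protocol. It is used only for workload.

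**Longest permitted wait as written.** If the week starts on receipt, the ceiling is about 7 days to reading, and the discussion with the PI follows. If it starts at REDCap entry, a paper form could wait longer than 7 days from receipt.

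**Is there a faster route elsewhere in the text?** None is described: no automatic scoring, no alert and no same-day check. The weekly RC and PI meeting (General Notes) cannot bring up a score that nobody has read.

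**Longest permitted wait under the proposal.** A form submitted early on one weekday and answered late on the next working day waits just under 2 days. From early Friday to late Monday it waits just under 4 days. An alert cannot be answered without being read, so these limits also bound the time to reading.

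| Case | Now | Proposed | Approximate cut |
|---|---|---|---|
| Midweek | 7 days | just under 2 days | 7 − 2 = 5 days |
| Friday to Monday | 7 days | just under 4 days | 7 − 4 = 3 days |

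**Workload, with no assumption about how many score high**

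- 9 months = 39 weeks: 86 / 39 = 2.2 baseline forms a week.
- 9 + 3 = 12 months = 52 weeks: 86 / 52 = 1.7 baseline forms a week.
- Items per form: 14 + 6 = 20. If every form were on paper, 2.2 × 20 = 44 items a week, or 1.7 × 20 = about 34.
- With 3-month forms arriving at the same rate and no drop-out: 2 × 2.2 = 4.4 forms a week.

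These are averages. If every form raised an alert, alerts would average the same, but enrollment can cluster and single weeks can be busier.

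**Number affected.** The documents give no distribution of HADS or K6 scores in this population, so the number above either cut-off cannot be determined.

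**The case against.** The strongest case against is that the safeguard already exists. The protocol names a reviewer, a deadline, thresholds and a route to the PI, and the week is a ceiling that may rarely be reached. Nothing in the documents says a week is too long for these instruments. HADS is described as not diagnostic, and no self-harm item is described in either scale. Participants are clinic outpatients who keep their routine care. The text is a coordinator's working guide, and the consent and contact pages are not available here, so distress resources or urgent contacts may have been given there.

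Much of this stands, and it limits the claim. It does not remove it: a safety rule is judged by what it permits, and the urgency comes from the protocol's own trigger.

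Several stronger readings are tempting, and the documents do not support them:

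- **That the two steps contradict each other.** They do not. One limits when the form is read; the other governs what happens after reading.
- **That participants have no safety cover for a week.** The documents show only that no faster check of these scores is described.
- **That the delay differs by arm or biases the comparison.** Baseline forms are completed before randomization, so participants have no arm when they submit them.
- **That diagnoses are being missed.** The point concerns a distress trigger.

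The open HADS cut-off and the silence about the 3-month form are separate gaps. They belong here because the fix has to deal with them, but they do not lengthen the baseline window.

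**Conclusion.** The point holds as a modest, inexpensive improvement to participant safety. As written, a baseline score above the trigger may go unread for about 7 days, for any of the 86 planned enrollees. The 3-month form, with the same two scales, has no stated review or escalation rule at all. A next-working-day rule would cut the baseline ceiling by roughly 3 to 5 days.

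This rests on two assumptions: that the week starts on receipt, and that next working day is a reasonable target. The second is a judgement, and a public holiday would lengthen the wait. The benefit in participants helped is unquantified. Bias, power and the planned analysis are unaffected, and nothing here is an error in the analysis.

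**What to change.** Apply the change to HADS and K6 only; the one-week window can stay for the other items.

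1. Score both scales automatically in REDCap, alert the RC and PI on submission, and require an answer by the next working day, with a named deputy for absences.
2. Score the two scales by hand on the day a paper form is received, because an alert cannot fire until the form has been entered.
3. Set the K6 alert at the stated cut-off now. Settle the HADS cut-off, then set its alert.
4. Apply the same rule to the 3-month form.

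The cost is a REDCap build and prompt attention from existing staff. The protocol already says "RC will assist in the creation of a secure electronic database and maintain data using REDcap", although it does not say who would build the alerts, so calling the build small is a judgement. The load averages about 1.7 to 2.2 baseline forms a week, and up to about 4.4 with 3-month forms, with busier weeks possible.

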- At 3 months, RC will deliver the 3-mo questionnaire. At least 5 telephone and email attempts will be made to obtain responses, unless patients opt out.
- RC will provide gift cards (\$50) to participants ahead of final questionnaire completion.

Intervention group:

- Within 2 weeks of baseline data collection, RC will schedule an initial research visit to introduce PRISM and create a completion plan.
- Patients will subsequently schedule and participate in five 30-50-minute sessions (four core PRISM skills sessions and one ACP session), followed by one 30-50-minute "Coming Together" session with patients and their caregivers. ~~Ideally, the first session is conducted~~

~~in person~~ [changed Jan 2023] Sessions will occur using telephone or video chat. Each subsequent session will occur within 1-2 weeks of the previous session (=intervention completion by 3 months). At least 5 telephone and email attempts will be made to schedule sessions, unless patients opt out.

- After completing PRISM, RC will deliver the 3-mo questionnaire. At least 5 telephone and email attempts will be made to obtain responses, unless patients opt out.
- RC will provide gift cards (\$50) to participants ahead of final questionnaire completion. Study-related activities (such as parking; case-by-case basis, discuss with PI) will also be reimbursed.
- RC will conduct “exit interviews” with a subset of PRISM participants (discuss with PI) to gather feedback about the experience/intervention. A modest gift card will be provided to interview participants.
- RC will keep notes on patient interactions and any feedback or comments provided during or related to sessions. This will occur in a separate “PRISM Memos/Feedback” document.

Statistical Analysis Plan

(As Published in *Contemporary Clinical Trials*, October 2024;
<https://doi.org/10.1016/j.cct.2024.107638>)

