Our primary aim is to describe feasibility, defined by the proportion of patients who a) enroll in the study among those who are eligible during the recruitment period, and b) complete the PRISM intervention among those randomized to that arm. We anticipate 70% enrollment and retention rates. We will also gain insight into feasibility from a qualitative content analysis of transcribed exit interview data. We anticipate that transcriptions will be reviewed by two study team members, using an inductively developed coding matrix to identify and organize topics discussed. Finally, the research coordinator and PRISM coach will provide an assessment of feasibility from the interventionist standpoint, summarizing study conduct adaptations and barriers that must be addressed in future studies, or if PRISM were to be implemented at scale in the ACHD population.

Additionally, we will evaluate the efficacy of the PRISM intervention to increase resilience in this population. We will evaluate the difference in mean resilience at 3 months after randomization between participants randomized to PRISM and participants randomized to usual care, following the intent-to-treat principle. We will adjust for resilience score at randomization, via a linear regression model, as resilience at randomization and 3 months later (after the intervention period) will likely be highly correlated and thus the adjustment will improve our precision. In exploratory analyses, we will evaluate the effect of the PRISM intervention on QOL, psychological distress, perceived competence for health care management, and comfort with advance care planning using analogous analyses.

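### The follow-up questionnaire is triggered by the calendar in usual care but by finishing PRISM in the intervention arm, which leaves PRISM non-completers with no delivery step

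*Combined protocol and SAP*

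**What the plan says.** The protocol gives the follow-up questionnaire two different triggers. For usual care (Usual Care group): "At 3 months, RC will deliver the 3-mo questionnaire". For the intervention arm (Intervention group): "After completing PRISM, RC will deliver the 3-mo questionnaire".

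The measures table lists the CD-RISC 10 and the other patient-reported outcomes at "Patient; enrollment & 3 months" and does not separate the arms. The SAP's efficacy paragraph compares mean resilience 3 months after randomisation between the arms as randomised, by intent to treat and with adjustment for baseline resilience. The exploratory outcomes are to be analysed in the same way.

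Two places suggest that the authors regard the end of PRISM and the 3-month point as the same moment. The Intervention group section says "Each subsequent session will occur within 1-2 weeks of the previous session (=intervention completion by 3 months". The SAP, when justifying the baseline adjustment, describes the 3-month measurement as coming after the intervention period. No sentence says which anchor governs if the two differ, no assessment window is given, and no step covers a PRISM participant who stops early. The sentence requiring at least five contact attempts comes after delivery, so it does not itself trigger delivery.

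**The concern.** An intent-to-treat comparison needs outcomes sought from everyone randomised, at the same time in both arms. The PRISM instruction, taken as written, makes outcome collection in one arm depend on adherence and lets that arm be measured sooner, close to its last contact with the interventionist. The General Notes tell the coordinator "RC will keep complete and secure study records and adhere to protocol fidelity", so a literal reading is a realistic one.

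Non-completion is also expected: the SAP makes PRISM completion among those randomised to it part (b) of the feasibility definition.

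At stake is the between-arm comparison of resilience, and with it the exploratory outcomes, through selection (completers only) and timing. Baseline adjustment does not correct timing and corrects selection only in part. Both feasibility proportions, enrolment and PRISM completion, can be computed whatever the questionnaire timing.

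**Working it through.** **The plan's own figure.** The sample-size text says "To achieve complete data for 60 participants, we anticipate enrolling 86 patients, 43 in each arm". The SAP says "We anticipate 70% enrollment and retention rates". With 30% loss, 60 / 0.70 = 85.7, rounded up to 86; per arm, 30 / 0.70 = 42.9, rounded up to 43. The figure reproduces.

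**Timing.** Inputs from the Intervention group section: an introductory visit 0–2 weeks after baseline (assuming it takes place in that window; the text says only that it is scheduled), six sessions (five plus the family session), and spacing of 1–2 weeks. Randomisation follows baseline measures, so baseline is taken as time zero. Three months = 365.25 / 12 × 3 / 7 = 13.0 weeks.

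| Reading | Formula | Range | Mid-range (visit week 1, spacing 1.5) | Mid-range against 13.0 |
|---|---|---|---|---|
| Session 1 at the introductory visit | visit + 5 × spacing | 0 + 5 = 5 to 2 + 10 = 12 | 1 + 7.5 = 8.5 | 4.5 weeks early |
| Session 1 one interval later | visit + 6 × spacing | 0 + 6 = 6 to 2 + 12 = 14 | 1 + 9 = 10 | 3 weeks early |

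The second reading fits "Patients will subsequently schedule and participate in five 30-50-minute sessions" better. Delivery at completion could therefore fall from 8 weeks before to 1 week after the usual-care point. These are permitted timings, not predicted ones.

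**Participants without a trigger.** If 70% retention is read as PRISM completion (an assumption), 0.30 × 43 = 12.9, about 13.

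**Illustrative bias.** Assumptions not in the documents: 30 analysed per arm, usual-care loss at random, no PRISM non-completer measured, baseline-to-3-month correlation r of 0.5 or 0.7, two-sided 5% test, and a completer/non-completer gap g in SD units. The standard error is √(2/30) × √(1 − r²) = 0.224 SD (r = 0.5) or 0.184 SD (r = 0.7). Type I error is the normal probability of exceeding ±1.96 when the standardised mean is bias / SE.

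(a) The gap g remains after baseline adjustment: bias = 0.30g.

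| g | Bias | Type I error, r = 0.5 | Type I error, r = 0.7 |
|---|---|---|---|
| 0.25 | 0.075 | 6% | 7% |
| 0.50 | 0.150 | 10% | 13% |
| 0.75 | 0.225 | 17% | 23% |

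(b) The same raw gap is present at baseline and at 3 months: bias = 0.30g(1 − r).

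| g | Bias, r = 0.5 (type I error) | Bias, r = 0.7 (type I error) |
|---|---|---|
| 0.25 | 0.038 (5%) | 0.023 (5%) |
| 0.50 | 0.075 (6%) | 0.045 (6%) |
| 0.75 | 0.113 (8%) | 0.068 (7%) |

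A simulated baseline-adjusted regression with 30 per arm (8,000 runs per cell) agreed within 1 percentage point.

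**What calendar timing would recover.** If a fraction f of non-completers answer, non-completers make up 0.3f / (0.7 + 0.3f) of those analysed, and the bias removed is g times that share. For g = 0.5 in case (a), where the bias is 0.15 SD:

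| f | Bias removed (SD) |
|---|---|
| 0 | 0 |
| 0.25 | 0.5 × 0.075 / 0.775 = 0.048 |
| 0.5 | 0.5 × 0.15 / 0.85 = 0.088 |
| 1 | 0.5 × 0.30 / 1.00 = 0.150 |

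**The case against.** The strongest reply is that the PRISM instruction gives only the order of steps. The questionnaire is named by calendar time, completion is expected by 3 months, the SAP places the 3-month measurement after the intervention, and nothing says delivery is immediate on completion. The coordinator's document also contains the measures table, and the coordinator meets the principal investigator weekly. On this reading one sentence is loose and the rest of the plan is consistent.

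That reading is fair as an account of intent, and the text does not show a plan to drop non-completers. It does not remove the problem. A completion bound of 3 months is an upper limit and not a date, and the longest permitted schedule passes it. Read purely as sequence, the instruction still has no step for someone who never completes.

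The objections to the numbers have more force:

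- The values of g and r, the 5% test and random usual-care loss are all assumptions; the SAP states no significance level.
- The plan inflates both arms for the same 30% loss, so the share of missing data due to this wording cannot be derived. If usual-care non-responders differ in a similar way, the biases partly cancel.
- The 23% corner pairs g = 0.75 with r = 0.7. The residual SD is then √(1 − 0.49) = 0.71, so the gap is about 1.05 residual SDs, which is extreme.
- No bias has been derived from the timing difference itself.
- If no non-completer answers, the correction recovers nothing.

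All of these stand. They limit the figures to illustrations and leave the textual conflict as it is.

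**Conclusion.** The concern holds. The plan has conflicting rules for one assessment, and the PRISM rule gives non-completers no delivery step. The conflict rests on the text alone. The count of about 13 of 43 rests on reading the retention figure as completion. The size of any bias is unknown: the illustrations run from near nothing to about 0.2 SD, which matters in a comparison whose standard error is itself about 0.2 SD. The documents do not show that any assessment was mistimed or any non-completer left unmeasured.

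This should be fixed, with medium confidence about its practical effect. The efficacy comparison is secondary in a pilot, but the stated hypothesis includes improved resilience relative to usual care.

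**What to change.** Replace the PRISM-arm sentence with one rule for both arms: the coordinator delivers the 3-month questionnaire to every randomised participant 3 months after the randomisation date, with the same window and the same contact attempts, whether or not PRISM sessions have been completed. State the window, since the plan gives none. Record the number of sessions completed by that date. Amend the SAP's remark that the measurement follows the intervention period, so that it allows for participants still in sessions.

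The cost is a sentence of protocol wording, a matching edit in the SAP and a REDCap reminder keyed to the randomisation date. The downside is small: a few slower participants are measured before their last session, which is still the intent-to-treat quantity the SAP names. No treatment changes, and the enrolment target of 86 stays as it is.

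If data collection is over, add one descriptive table giving actual time from randomisation to assessment by arm and the number of PRISM non-completers with outcome data, and qualify the intent-to-treat label accordingly.

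### Three-month data return, the rate behind the 86, is not a feasibility outcome, and the protocol does not say that patients who stop PRISM are sent the 3-month questionnaire

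*Combined protocol and SAP*

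**What the plan says.** The Statistical Analysis Plan makes feasibility the primary aim and names two proportions. The first, (a), is the share of patients who "enroll in the study among those who are eligible during the recruitment period". The second, (b), is the share who "complete the PRISM intervention among those randomized to that arm". The sentence that follows reads "We anticipate 70% enrollment and retention rates". It does not say what is retained, in which arm, or up to what time. Exit interviews and an assessment by the coordinator and coach complete the feasibility material.

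The protocol, under Participant Enrollment, sets a target of 60 patients, 30 in each group, and adds: "To achieve complete data for 60 participants, we anticipate enrolling 86 patients, 43 in each arm".

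Under Study Measures and Data Collection, the two arms have different instructions for the outcome questionnaire. Usual Care group: "At 3 months, RC will deliver the 3-mo questionnaire". Intervention group: "After completing PRISM, RC will deliver the 3-mo questionnaire". Both arms get at least five contact attempts.

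The efficacy analysis in the Statistical Analysis Plan compares mean resilience 3 months after randomization between the randomized groups, by intent-to-treat and adjusted for the score at randomization.

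**The concern.** Two quantities are in play, and the plan has a single undefined word for them. PRISM completion is adherence: it exists in one arm and concerns sessions. Complete 3-month data is outcome retention: it exists in both arms and concerns a questionnaire. A PRISM completer may fail to return the questionnaire, a patient who stops PRISM may return it, and a usual-care patient has no sessions to complete.

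The sample size depends on outcome retention, but the feasibility aim reports only adherence. A pilot should give a later trial its expected loss to follow-up in each arm, and this plan does not name that as a result.

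The delivery instructions make this more than a matter of labels. Taken literally, a patient who stops PRISM never reaches the event that triggers the questionnaire. Those patients belong to the intent-to-treat comparison. If they are not sent it, PRISM-arm data come mainly from people who finished, while usual-care data come from anyone who responds. Proportion (b) would look the same whether or not that happened.

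**Working it through.** **Inputs from the documents.** Target with complete data: 60, or 30 per group. Planned enrolment: 86, or 43 per arm (both from Participant Enrollment). Anticipated enrolment and retention: 70% (Statistical Analysis Plan).

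**Step 1. Reproduce the 86.** Enrolment = target / (expected proportion with complete data), rounded up.
- Total: 60/0.70 = 85.7, giving 86.
- Per arm: 30/0.70 = 42.9, giving 43, and 2 × 43 = 86.
- Back-check: 60/86 = 30/43 = 69.8%.
- The alternative of adding 30% to the target gives 60 × 1.30 = 78, which does not match.

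The sample-size text does not print 70%. It is inferred, but it reproduces both figures and equals the only retention rate in the documents. The 86 therefore implies about 70% complete data in each arm, usual care included.

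**Step 2. Look for that rate among the feasibility outcomes.**

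| Feasibility source | Denominator | Gives 3-month data return? |
|---|---|---|
| (a) enrolment | eligible patients | No |
| (b) PRISM completion | PRISM arm only | No |
| Exit interviews | subset of PRISM participants | No |
| Coordinator and coach assessment | not a proportion | No |

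**Step 3. See how far data return can move while (b) stays at 70%.** Let r_c be questionnaire return among PRISM completers, r_n return among non-completers, and u return in usual care. None of these is in the documents; all are assumptions.

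PRISM-arm data = 43 × (0.70 r_c + 0.30 r_n). Usual-care data = 43 × u.

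With u = 0.90, usual care has 43 × 0.90 = 38.7:

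| r_c | r_n | PRISM return | PRISM with data | Gap (usual care minus PRISM) | Total |
|---|---|---|---|---|---|
| 1.00 | 0 | 70% | 30.1 | 20 points | 68.8 |
| 1.00 | 0.50 | 85% | 36.55 | 5 points | 75.25 |
| 0.90 | 0 | 63% | 27.1 | 27 points | 65.8 |
| 0.90 | 0.90 | 90% | 38.7 | 0 points | 77.4 |

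Proportion (b) is 70% in every row. With u = 0.70, the first row totals 30.1 + 30.1 = 60.2 and the third 27.1 + 30.1 = 57.2. Whether 60 is reached therefore depends on completers' return as well.

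**Step 4. Why report by arm.** If 60% of the PRISM arm and 80% of usual care have data, the total is 25.8 + 34.4 = 60.2. That is 70% overall, yet the PRISM arm is below its planned 30.

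**Step 5. Precision of the missing proportion.** At the planned values, Wilson 95% intervals are 54.9% to 81.4% per arm (30/43) and 59.4% to 78.5% overall (60/86).

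**The case against.** The strongest reply is that retention may simply mean trial retention in both arms, which is the 70% that reproduces 86. On that reading nothing is mislabelled. A reader might infer that the plan expressly equates retention with PRISM completion. Position in the paragraph suggests it, but the sentence does not say so, and the point does not need it. On either reading, no listed feasibility proportion measures 3-month data return.

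Second, the plan describes feasibility and anticipates 70%; it sets no threshold or test. A reader might infer that a go/no-go decision would be taken on the wrong proportion. The documents contain no such decision.

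Third, return by arm could be computed from data that will exist anyway, since the CD-RISC 10 is scheduled at enrolment and 3 months. This stands, and if labelling were the only issue the point would be a clarification.

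Fourth, the PRISM-arm instruction may only describe timing when all goes well. The protocol expects its session schedule to finish by 3 months, and the measures table gives 3 months for all patients. That is a fair reading, and staff may well contact non-completers. But the text gives no instruction for them, and an intent-to-treat analysis should not depend on how a coordinator fills that gap.

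**Conclusion.** The concern holds as a gap in definition, follow-up instruction and reporting. The rate implied by the 86, about 70% complete 3-month data in each arm, is not a named feasibility result. The protocol's wording could leave PRISM non-completers without the outcome questionnaire, and (b) would not reveal a resulting difference in loss between arms.

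The size is illustrative. With 90% usual-care return and 70% PRISM completion, the gap is 0 to 27 points over the scenarios shown. It turns on return among both completers and non-completers, neither of which the documents give.

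Two stronger conclusions are not supported. The enrolment figure is not wrong: it follows from its implied rate. Nor do the documents show that non-completers are excluded or that differential loss will occur; they leave it open.

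**What to change.** 1. **Protocol, Study Measures and Data Collection.** Reconcile the two delivery instructions with the intent-to-treat analysis. State that all randomized patients, including those who stop PRISM, are sent the questionnaire at 3 months after randomization, with the same contact attempts in both arms.
2. **Statistical Analysis Plan.** Define retention as return of an evaluable 3-month CD-RISC 10 among all randomized. Add it as feasibility proportion (c), overall and by arm with confidence intervals, and attach the 70% behind the 86 to it.
3. **Statistical Analysis Plan.** Keep (b), reported separately under the name adherence.

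The cost is a few added or reworded sentences, one more descriptive proportion and a few more questionnaire contacts. Sample size, instruments and efficacy model do not change. If data collection has ended, items 2 and 3 need only existing data, and item 1 becomes a statement of how non-completers were in fact followed.
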